4.4.2 Confirmation of the Indistinguishability of the Study Drugs

The indistinguishability in appearance of the study drugs and their packages will be checked by the trustees for manufacturing and packaging or storing the study drugs at the following time points, and will be determined by the Quality Assurance Quality Technology department:

- Before delivery to the study site: Checked by the trustee for manufacturing and packaging the study drugs
- Between completion of the study drug administration and treatment code breaking: Checked by the trustee for storing the study drugs

4.4.3 Retention of the Assignment Schedule and Procedures for Treatment Code Breaking

1) Retention of the Treatment Codes

The person responsible for study drug randomization will prepare and separately seal one original and one copy of each treatment code. The person responsible for study drug randomization will retain the original, while the Sponsor will retain the copy, of the treatment

code until the time of the treatment code breaking. In addition, the person responsible for study drug randomization will prepare the treatment codes for emergency and seal them after randomization. The sealed treatment codes for emergency will be retained by the person responsible for treatment codes for emergency. The treatment codes for emergency will be able to be opened individually, and will be controlled by the person responsible for treatment codes for emergency via a Web-based system.

2) Treatment Code Breaking

After completion of administration of the study drugs and after the eCRF data are locked and handling of the data is decided, the person responsible for study drug randomization will open the original assignment schedule. The person responsible for study drug randomization will then submit the original assignment schedule to the Sponsor and document the submission record.

4.4.4 Breaking the Treatment Code for Emergency

In any medical emergency where the study drug needs to be identified to be either gabapentin enacarbil tablets 300 mg or placebo, the investigator/sub-investigator may request the sponsor's responsible person to break the treatment code for emergency for a given subject. The sponsor's responsible person will judge appropriateness of breaking the treatment code for emergency and, if appropriate, open the code in accordance with the "Procedures for emergency code breaking for gabapentin enacarbil post-marketing clinical study." The investigator/sub-investigator, sponsor's responsible person, and the person responsible for treatment codes for emergency will communicate with each other to allow for prompt breaking of the treatment code for emergency. The sub-investigator may request for breaking the treatment code for emergency, in principle after prior agreement of the investigator. However, if prior agreement of the investigator cannot be obtained, the sub-investigator will promptly notify the investigator of the request.

4.4.5 Breaking the Treatment Code by the Sponsor

The Sponsor may break the treatment code for subjects who experience an SUSAR, in order to determine whether the individual case or a group of cases requires expedited regulatory reporting. Individual Emergency Codes will be provided to the limited staff who are responsible to break the codes for all SUSAR cases for reporting purposes.

The treatment code for each randomized subject will be provided by the person managing treatment codes for emergency or the Interactive Response Technology (IRT) in the event of a medical emergency requiring knowledge of the treatment assigned to the subject. The time, date, subject number, and reason for obtaining any of these codes, and therefore breaking the blind, must be documented in the study file. They must only be requested by the investigator or other persons designated as sub-investigators. The need for expedited regulatory reporting of the SUSAR will be judged only by the designated personnel of the safety management

department. No subjects or other study personnel will be made aware of the treatment given to any subject unless a medical emergency necessitates such disclosure.

Unblinding of the study medication should only be considered for subject safety or when clinical therapeutic decisions are contingent upon knowing the blinded study drug assignment. Any unblinding by the study staff must be reported immediately to the Sponsor and must include an explanation of why the study medication was unblinded. If possible, the Sponsor should be contacted prior to unblinding of the study medication.

4.5 Assignment and Allocation

The person responsible for study drug randomization will prepare the treatment codes for randomization of the study drug for the double-blind period, and retain them under lock and key until the time of treatment code breaking.

Stratified allocation will be performed with stratification factors of age (< 50 years and \geq 50 years) at the start of the run-in period and estimated creatinine clearance (\geq 60 to < 90 mL/min and \geq 90 mL/min) at the start of the run-in period, to minimize imbalance in subject characteristics between the treatment groups to allow for proper comparison. The patient registration center will assign the drug numbers to the subjects in accordance with the patient registration procedures.

5 TREATMENTS AND EVALUATION

5.1 Dosing and Administration of Study Drug and Other Medications

5.1.1 Dose, Dosage Regimen, and Administration Period

[Dose]

- Gabapentin enacarbil 600 mg group: 600 mg/day of gabapentin enacarbil
- Placebo group: 0 mg/day of gabapentin enacarbil

[Dosage regimen and administration period]

Two tablets will be administered orally once daily after the evening meal.

Treatment group	Run-in period (1 week)	Treatment period (12 weeks)		Follow-up period (1 week)
		Upward titration period (1 week)	(11 weeks)	
Placebo group (0 mg/day)	○○	○○	○○	○○
600 mg group (600 mg/day) (Patients with an estimated creatinine clearance of \geq 90 mL/min at the start of the run-in period)		●●	●●	
600 mg group (600 mg/day) (Patients with an estimated creatinine clearance of \geq 60 to < 90 mL/min at the start of the run-in period)		○●	●●	

●: Gabapentin enacarbil tablets 300 mg. ○: Placebo matching gabapentin enacarbil tablets

5.1.2 Increase or Reduction in Dose of the Study Drug

No dose reduction will be performed in this study. For patients in the gabapentin enacarbil group with an estimated creatinine clearance of \geq 60 to < 90 mL/min at the start of the run-in period, the starting dose will be 300 mg given for 1 week, and the dose will be increased to 600 mg with careful monitoring of the subject's condition for possible occurrence of AEs.

5.1.3 Previous and Concomitant Treatment (Medication and Non-medication Therapy)

5.1.3.1 Previous Treatment (Medications and Non-medication Therapies)

Use of the following drugs before the start of the run-in period will require the specified washout period:

- 1) Dopamine agonists, dopamine preparations, gabapentin: \geq 7 days
- 2) Opioids, benzodiazepines (for only if used to treat RLS), long-acting dopamine agonists: \geq 14 days

Previous medication and previous non-medication therapy are defined respectively as the medication and non-medication therapy used by the day before the start of the run-in period. In terms of all previous medications and therapies up to 28 days before the start of the run-in period, the data below will be collected and recorded on the eCRF. No recording on the eCRF will be required for drugs used to treat common cold or other transient conditions or past otorhinolaryngologic diseases, dental diseases, skin diseases, ophthalmologic diseases, etc., or for pre-treatment before endoscopy, etc.

- Previous medication: name of the drug, route of administration, duration of treatment, therapy dates, reason for use
- Previous non-medication therapy: name of the therapy, duration of treatment, therapy dates, reason for use

5.1.3.2 Concomitant Treatment (Medication and Non-medication Therapy)

For all drugs and therapies used after the start of the run-in period through the end of the study period, the following data will be recorded on the eCRF:

- Concomitant medication: name of the drug, route of administration, therapy duration, therapy dates, reason for use
- Concomitant non-medication therapies: name of the therapy, therapy duration, therapy dates, reason for use

[Excluded concomitant medications/therapies, etc.]

- 1) Concomitant use of the following drugs will be prohibited from 14 days before the first day of the run-in period through the end of the study period:
 - Benzodiazepines (for only if used to treat RLS): clonazepam, etc.
 - Opioids: codeine, oxycodone, morphine, etc.
 - Long-acting dopamine agonists: cabergoline, etc.
- 2) Concomitant use of the following drugs will be prohibited from 7 days before the first day of the run-in period through the end of the study period:
 - Dopamine agonists: pramipexole (BI-Sifrol), talipexole, rotigotine (Neupro Patch), ropinirole, etc.
 - Dopamine preparations: levodopa/carbidopa combined drug, etc.
 - Gabapentin: Gabapen
 - Gabapentin enacarbil: Regnite
 - Pregabalin: Lyrica
- 3) Concomitant use of the following drugs will be prohibited from the first day of the run-in period through the end of the study period:
 - Dopamine receptor inhibitors: Primperan (metoclopramide), Nauzelin (domperidone), etc.
 - Central depressants (hypnotics, antianxiety drugs, antipsychotic drugs, antidepressants, antimanic drugs, antiepileptic drugs)
 - Magnesium preparations^{*1}, iron preparations^{*1}, folic acid^{*1}, vitamin B12 preparations^{*1}
 - Other investigational products or post-marketing clinical study drugs

^{*1}These apply to prescription drugs

4) The following drugs are prohibited for concomitant use from 7 days before a visit (day of IRLS score assessment) until the time of the IRLS score assessment at the visit, between the first day of the run-in period and the end of the study period:

- Antihistamines

[Rationale for the excluded concomitant medications/therapies, etc.]

These drugs/therapies are prohibited to avoid possible effects on evaluation of the efficacy of gabapentin enacarbil.

5.1.4 Treatment Compliance

The treatment compliance status of each subject will be recorded on the eCRF at each visit.

At dispensing of the study drug to the subject, the investigator/sub-investigator and the study drug storage manager will explain how to take the study drug, with particular caution to the following:

- 1) The subject must never take more one dose at a time, even if a dose of the study drug has been missed.
- 2) The subject must bring the remaining study drug and empty bottles at the next visit.

The investigator/sub-investigator or clinical research coordinator will record each subject's treatment compliance status during the study period on the eCRF, based on the study drug prescription date, number of the study drugs prescribed, number of the study drugs retrieved, number of the study drugs lost, start and end date of administration, interview with the subject, etc. If the compliance rate is judged to be problematic, the reason will be investigated, and instruction on proper medication will again be given to the subject to improve the compliance rate.

5.1.5 Emergency Procedures and Management of Overdose

If gabapentin enacarbil overdose has caused certain symptoms, the investigator/sub-investigator will perform emergency treatment according to the symptoms, and secure the safety of the subject. Oral administration of gabapentin enacarbil up to 6 g has been reported overseas. Typical symptoms of overdose have been psychomotor retardation, vertigo, sedation, and somnolence. In the event of overdose, symptomatic treatment should be given. Gabapentin, which is the active metabolite of gabapentin enacarbil, can be removed by hemodialysis. Implementation of hemodialysis should be considered depending on the symptoms.

5.1.6 Criteria for Continuation of Treatment

Study treatment will not be extended in this study.

5.1.7 Restrictions During the Study

The investigator/sub-investigator will explain the compliance rules to the subjects, with particular caution to the following, when explaining how to take the study drug, etc.:

- Subjects will visit the study site according to the schedule stipulated in the protocol, and undergo scheduled tests and other procedures.
- Subjects are not allowed to take drugs that may affect assessment of the drug efficacy on the target disease (excluded concomitant medications) during the study period. The use of magnesium preparations, iron preparations, over-the-counter drugs or supplements containing folic acid or vitamin B12, and dietary supplements should be avoided as far as possible. Subjects are not allowed to take other drugs (including over-the-counter drugs such as combination cold remedies) at their own discretion without approval by the investigator, etc. If subjects desire to use such drugs, they should consult the investigator, etc. first.
- Subjects should notify the investigator/sub-investigator as far as possible beforehand if they will visit another hospital/department, newly visit another hospital/department, or use other drugs, including over-the-counter drugs, than those prescribed by the investigator/sub-investigator. If not beforehand, the investigator/sub-investigator should be notified afterwards.
- Subjects should use contraceptives during the study period, in line with inclusion criteria 8 to 10.
- Subjects with a history of regular alcohol consumption should avoid drinking alcohol during the study period as instructed by the investigator/sub-investigator.
- Subjects should store the study drug at room temperature.
- Subjects should take the study drug once daily after the evening meal, with water and without chewing or crushing the tablet. If a dose is missed after the evening meal, the dose may only be taken before bedtime.
- Subjects should take each dose of the study drug as instructed by the investigator/sub-investigator. When a dose is missed, the missed dose should not be taken together with the next dose.
- The study drug should not be taken with alcohol.
- Subjects should return any remaining portions of the study drug due to missed doses, etc., to the investigator/sub-investigator, and report the compliance status.
- If a subject has stopped taking the study drug at his or her own discretion, the subject should visit the study site as early as possible to undergo physical assessment by the investigator/sub-investigator.

Since the study drug may cause dizziness or sleepiness, subjects should be advised to exercise caution when working in high places, driving, or operating potentially hazardous machinery, etc.

5.2 Demographics and Baseline Characteristics

5.2.1 Demographics

The investigator/sub-investigator will collect the data below at the time of informed consent (or at provisional registration) via a medical interview, etc., and check the eligibility (see **Section 3.2 Inclusion Criteria** and **Section 3.3 Exclusion Criteria**). At the time of formal registration, the investigator/sub-investigator will again check the eligibility (see **Section 3.2 Inclusion Criteria** and **Section 3.3 Exclusion Criteria**) and enter the details on the eCRF.

- 1) Sex, date of birth
- 2) Height, body weight
- 3) Family history (RLS)
- 4) Date of informed consent

5.2.2 Medical History

At selection of potential subjects, the investigator/sub-investigator will collect information on past diseases and concurrent diseases on the basis of existing medical records. Also at the time of informed consent as necessary, information on past diseases and concurrent diseases will be collected by way of medical interview with each potential subject. Patients should be excluded from this study if the collected information meets any of the exclusion criteria.

- 1) Past diseases
 - (1) Diseases that already resolved at the start of the run-in period are regarded as past diseases.
- 2) Concurrent diseases
 - (1) Diseases that have not resolved at the start of the run-in period are regarded as concurrent diseases.
 - (2) For the concurrent diseases judged by the investigator/sub-investigator to be present at the start of the run-in period, the diagnoses will be entered on the eCRF.

5.2.3 Diagnosis of the Target Disease, Severity, and Duration of Disease

The investigator/sub-investigator will collect information on the diagnosis, time of onset, and current symptoms (according to the RLS diagnostic criteria established by the International RLS Study Group) by way of medical interview, etc. at the time of informed consent (or at provisional registration), and enter the following data on the eCRF:

- Time of onset of the target disease (RLS)

5.3 Efficacy Assessment

The following data will be collected and entered on the eCRF:

Both the investigator/sub-investigator and the subjects will assess symptoms without referring to previous assessments. The investigator/sub-investigator should not answer questions from the subjects regarding previous assessments.

[Primary endpoint]

IRLS score: Week -1 (run-in period), Week 0 (baseline), Week 1, Week 2, Week 4, Week 6, Week 8, Week 10, Week 12, Week 13 (follow-up period), discontinuation

[Secondary endpoints]

- 1) ICGI and PCGI: Week 1, Week 2, Week 4, Week 8, Week 12, Week 13 (follow-up period), discontinuation
- 2) Pittsburgh Sleep Quality Index: Week 0 (baseline), Week 4, Week 8, Week 12, discontinuation
- 3) Athens Insomnia Scale: Week 0 (baseline), Week 4, Week 8, Week 12, discontinuation
- 4) RLS Pain score: Week -1 (run-in period), Week 0 (baseline), Week 1, Week 2, Week 4, Week 6, Week 8, Week 10, Week 12, Week 13 (follow-up period), discontinuation
- 5) EQ-5D-5L: Week 0 (baseline), Week 4, Week 8, Week 12, discontinuation

5.4 Safety Assessment

The following data will be collected and entered on the eCRF:

5.4.1 Vital Signs

Vital signs (sitting blood pressure and sitting pulse rate): Week -1 (run-in period), Week 0 (baseline), Week 1, Week 2, Week 4, Week 6, Week 8, Week 10, Week 12, discontinuation

5.4.2 Adverse Events

Abnormal findings noted after the start of the run-in period will be collected. See **Section 5.5 Adverse Events and Other Safety Aspects** for information regarding AE collection and data handling.

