MedDRA/J	Medical Dictionary for Regulatory Activities/Japanese version
MITT	Modified Intention-to-Treat
NGSP	National Glycohemoglobin Standardization Program (HbA1c reporting units)
PCGI	Patient-rated Clinical Global Impression: Patient-rated Clinical Global Impression
PPS	Per Protocol Set

Abbreviations	Description of abbreviations
PT	Preferred Term
QOL	Quality Of Life
RBC	Red Blood Cell
RLS	Restless Legs Syndrome
SAE	Serious Adverse Event
SAF	Safety Analysis Set
SDV	Source Document Verification
SMO	Site Management Organization
SOC	System Organ Class
SOP	Standard Operating Procedure
SUSAR	Suspected Unexpected Serious Adverse Reactions
TBL	Total Bilirubin
TSH	Thyroid Stimulating Hormone
WBC	White Blood Cell

Definition of Key Study Terms

Term	Definition of terms
Follow-up period	The period from the start of administration of the study drug for the follow-up period to the final observation
Gabapentin	An antiepileptic drug synthesized in Germany in 1973; the active metabolite of gabapentin enacarbil
Gabapentin enacarbil	The active substance of Regnite Tablets; nonproprietary name of the drug
Registration failure	A subject who provided informed consent but did not fulfill the inclusion/exclusion criteria for formal registration and thus was not randomized or did not receive open-label study drug, or who withdrew consent during the run-in period.
Study period	The period from informed consent of the subject to completion of protocol-specified last evaluation/observation in the subject
Screening	A process of active consideration of potential subjects for enrollment in the study, conducted during the run-in period to determine the eligibility for the study
Enroll	To register or enter a patient into a clinical trial as a subject; NOTE: Once a subject is enrolled into the study, the clinical study protocol applies to the subject.
Subject	Study participant
Subject ID number	A number assigned to a subject who provided consent to participate in the study by signing the consent form
Endpoint	An attribute, phenomenon, or event that varies in quality or quantity and serves as a variable
Baseline	Measurement or finding obtained at a time point judged to be initiation of observation for comparison
Run-in period	The period from the start of administration of the study drug for the run-in period to before the start of administration of the study drug for the treatment period

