3.2 Inclusion Criteria

Subject is eligible for the study if all of the following apply:

At provisional registration:

1. Provided written informed consent using the informed consent form approved by the Institutional Review Board (IRB) prior to any study-related procedures (including discontinuation of excluded concomitant medications)
2. Male or female outpatient aged between ≥ 20 and ≤ 80 years at the time of consent

3. Patient with a diagnosis of RLS according to the International RLS Study Group diagnostic criteria for RLS (2014 update)
4. Had RLS symptoms for ≥ 15 days during the month prior to the start of the run-in period, or if on treatment for RLS, during the month prior to the start of that treatment
5. Has an International Restless Legs Syndrome Rating Scale (IRLS) score of ≥ 15 at the start of the run-in period
6. Has not taken dopamine agonists, dopamine preparations, gabapentin, gabapentin enacarbil, or pregabalin during at least one week before the first day of the run-in period
7. Has not received other treatments for RLS (opioids, benzodiazepines, long-acting dopamine agonists) during at least 2 weeks before the first day of the run-in period
8. Female subject must either:

Be of nonchildbearing potential:

- Postmenopausal (defined as no menstruation for at least 1 year) at the start of the run-in period, or
- Documented surgically sterile

Or, if of childbearing potential,

- Agree not to become pregnant during the study and for 28 days after the final study drug administration,
- And have a negative pregnancy test at the start of the run-in period
- And if heterosexually active, agree to consistently use two (one or both of which must be the barrier method) of the established forms of birth control* specified below, during the study period and for 28 days after the final study drug administration

*Established forms of birth control include:

- Correct usage of approved oral contraceptives
- Intrauterine device (IUD), intrauterine system (IUS), and other intrauterine instruments
- Barrier method with male condoms or female condoms
- Rhythm method (Knaus-Ogino method)

9. Female subject must agree not to breastfeed throughout the study period and for 28 days after the final study drug administration.
10. Female subject must not donate ova throughout the study period and for 28 days after the final study drug administration.
11. Agrees not to participate in another interventional study during the study period.

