5.5 Adverse Events and Other Safety Aspects

5.5.1 Definition of Adverse Events (AEs)

An AE is any untoward medical occurrence in a subject, temporally associated with the use of the study drug, whether or not considered related to the medicinal product. An AE can therefore be any unfavorable and unintended sign (including an abnormal laboratory finding), symptom, or disease (new or exacerbated) temporally associated with the use of the study drug.

For AEs noted during the run-in period, the event term, event onset date, time to event onset, event end date, severity, seriousness, other actions taken, and outcome will be entered on the eCRF.

For AEs noted during the treatment period, the event term, event onset date, time to event onset, event end date, severity, seriousness, action taken with the study drug, other actions taken, outcome, causal relationship to the study drug for the treatment period, and basis for the causality assessment will be collected and entered on the eCRF. However, the basis for the causality assessment will be required on the eCRF only for SAEs, AEs leading to discontinuation, and other AEs for which description of the basis is requested by the sponsor. In addition, as necessary, the investigator will record details of the treatment and clinical course in an appropriate document.

AEs during the follow-up period will also be collected, and the event term, event onset date, time to event onset, event end date, severity, seriousness, action taken with the study drug, causal relationship to the study drug for the treatment period, basis for the causality assessment, other actions taken, and outcome will be entered on the eCRF. However, the basis for the causality assessment will be required on the eCRF only for SAEs, AEs leading to discontinuation, and other AEs for which description of the basis is requested by the sponsor. In addition, as necessary, the investigator will record details of the treatment and clinical course in an appropriate document.

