5.5.6 Follow-up of Adverse Events

All AEs occurring during the study or before final observation are to be followed until they resolve or are judged to be no longer clinically significant, or until they become chronic to the extent that they can be fully characterized by the investigator.

If during AE follow-up, the AE progresses to an “SAE,” or if a subject experiences a new SAE, the investigator will immediately report the information to the Sponsor.

Even when the subject has not returned to normal or the level noted before administration of the study drug, if the investigator/sub-investigator judges that the follow-up of the subject is unnecessary or is completed and if the reason is appropriately specified in the source document, the follow-up may be unnecessary or completed.

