8 OPERATIONAL AND ADMINISTRATIVE CONSIDERATIONS

8.1 Procedure for Clinical Study Quality Control

8.1.1 Data Collection

The investigator, sub-investigator, or clinical research coordinator will enter data using an Electronic Data Capture (EDC) system. For efficient data collection, the investigator, sub-investigator, or clinical research coordinator should record data (including laboratory values, if applicable) on the eCRF within 5 days after the subject visit.

For questionnaires completed by subjects (i.e., PCGI, Pittsburgh Sleep Quality Index, Athens Insomnia Scale, RLS Pain score, EQ-5D-5L, and Epworth Sleepiness Scale), the investigator, sub-investigator, or clinical research coordinator will check the entries and enter these data into the eCRF. The subject will review the entries together with a clinical research coordinator after completing the questionnaires. If any entry is unclear, the subject will make an additional entry or correct the entry as necessary, and enter the date of the correction and sign or affix his or her personal seal.

The investigator, sub-investigator, or clinical research coordinator is responsible to ensure that all data on the eCRFs and queries are accurate and complete and that all entries are verifiable with source documents. These documents will be appropriately maintained by the site.

The monitor should verify the data on the eCRFs with source documents and confirm that there are no inconsistencies between them.

Laboratory tests will be performed at a central laboratory. Central laboratory data will be transferred electronically from the central laboratory to the Sponsor at predefined times. The central laboratory will provide the Sponsor with a complete copy of the data.

For the patients withdrawn before the start of the run-in period, the date of informed consent, minimum patient background data (sex, date of birth), and reason for withdrawal will be entered on the eCRF.

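### Events in a washout undertaken to enter the study fall after consent but before adverse event collection starts, and Table 1 places consent too late for these patients

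*Protocol*

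**What the plan says.** **Consent and washout.** Protocol 3.2, criterion 1, requires written consent "prior to any study-related procedures (including discontinuation of excluded concomitant medications". Criterion 6 bars dopamine agonists, dopamine preparations, gabapentin, "gabapentin enacarbil, or pregabalin during at least one week before the first day of the run-in period". Criterion 7 bars other RLS treatments, "opioids, benzodiazepines, long-acting dopamine agonists) during at least 2 weeks before the first day of the run-in period". Protocol 5.1.3 limits the benzodiazepine rule to use for RLS.

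**Study period.** The Definition of Key Study Terms gives it as "The period from informed consent of the subject to completion of protocol-specified last evaluation/observation in the subject". The run-in period, by contrast, begins with the first dose of run-in study drug.

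**Adverse events.** Protocol 5.4.2 states: "Abnormal findings noted after the start of the run-in period will be collected". Protocol 5.5.1 begins: "An AE is any untoward medical occurrence in a subject, temporally associated with the use of the study drug". It then sets out eCRF fields for events in the run-in, treatment and follow-up periods only.

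**Schedule.** Table 1 of the Protocol and the schedule in SAP section 2 mark informed consent and adverse event monitoring first in the Week -1 column (Day -7, window Day -10 to -7). There is no earlier column.

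**Early withdrawals.** Protocol 8.1.1 says: "For the patients withdrawn before the start of the run-in period, the date of informed consent, minimum patient background data (sex, date of birth"), and the reason for withdrawal, are entered on the eCRF. Adverse events are not among these items. They are among the items for patients withdrawn during run-in.

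**The concern.** The protocol asks some patients to give up a treatment so that they can be enrolled, takes consent for that step, and counts the days that follow as study time. It then begins safety recording only with the first placebo dose. If stopping the drug causes harm, the plan has no defined route for recording it as an adverse event.

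The protocol expects such patients. Inclusion criterion 4 provides for people on RLS treatment, and SAP 7.8 makes previous dopamine agonist use a subgroup. It also recognises that stopping can cause trouble. Exclusion criterion 2 refers to rebound after therapy, Protocol 2.2.2 adds a follow-up week to look for withdrawal symptoms after the study drug, and the grading criteria in 12.5 put withdrawal symptoms in Grade 3.

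Two things are at stake: the sponsor's sight of harm from a step that the study itself requires, and clear instructions to sites on when to take consent from a patient who needs a washout.

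**Working it through.** The plan states no figure on this point, so there is none to reproduce. The check is day arithmetic followed by a comparison of the sections.

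**1. When consent must be given.** Inputs: run-in visit window Day -10 to -7 (Table 1); minimum washouts of 7 and 14 days (criteria 6 and 7). The latest start of washout is the run-in day minus the minimum washout.

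| Run-in starts | 7-day washout starts no later than | 14-day washout starts no later than |
|---|---|---|
| Day -10 | -10 - 7 = Day -17 | -10 - 14 = Day -24 |
| Day -7 | -7 - 7 = Day -14 | -7 - 14 = Day -21 |

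Under criterion 1, consent comes before these days. For a patient who stops a drug in order to enter, consent is therefore due at least 7 or at least 14 days before that patient's Week -1 visit, the only place where Table 1 marks it. Both figures are lower limits, and the protocol sets no maximum.

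**2. Whether those days are study time.** They are, because the study period runs from consent.

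**3. Whether events in those days are adverse events.** Collection starts at run-in (5.4.2), the definition requires a temporal association with study drug (5.5.1), and no study drug is given before run-in. The earliest eCRF fields for adverse events belong to the run-in.

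**4. Whether SAE reporting covers them.** The sections point in different directions. Protocol 5.5.2 defines an SAE as a kind of AE, so it inherits the tie to study drug. Protocol 5.5.5 gives no start date. Protocol 5.5.6 says "All AEs occurring during the study or before final observation are to be followed until they resolve" and asks for immediate reporting of a new SAE; if the study is taken to start at consent, that reaches into the washout. Coverage is therefore unclear.

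**5. Where an event in the washout can appear.**

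| Course of the event | Where it can appear | What is missing |
|---|---|---|
| Leads to withdrawal before run-in | Reason for withdrawal (Protocol 6.1, 8.1.1), counted by primary reason (SAP 7.2.1) | Onset, severity, seriousness, causality, outcome |
| Still present at run-in | Diagnosis as concurrent disease (5.2.2); later worsening is an AE (5.5.1) | AE record of the original event; any link to the stopped drug |
| Begins and resolves within the washout, patient continues | At most as a past disease (5.2.2) | Any AE record |

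In the last row even the past-disease route is uncertain: 5.2.2 asks for that information at selection and, as needed, at consent, and both come before the washout.

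**The case against.** The case on the other side has real substance.

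- A reader might infer that washout harm is never recorded anywhere. The documents do not support that. Withdrawals before run-in carry a reason that the SAP tabulates, conditions present at run-in are entered by diagnosis, and SAP 7.2.2 codes and summarises medical history.
- A reader might infer that a serious event in the washout would go unreported. That is not shown either, since 5.5.5 has no start date and 5.5.6 can be read to include it.
- A reader might expect persisting washout symptoms to surface as run-in adverse events. Protocol 5.2.2 classes them as concurrent diseases, and only later worsening is an adverse event.
- The plan does contemplate consent before Week -1. Protocol 5.2.1 separates the time of consent from provisional registration, and 6.1, 8.1.1 and SAP 7.2.1 provide for people who leave before run-in. The flow chart is not shown in the text available and may place consent earlier.
- Patients already off a listed drug for other reasons meet criteria 6 and 7 with no study-driven washout. Exclusion criterion 2 removes those with known augmentation or rebound on dopamine agonists.
- Starting collection with the first study-drug period agrees with the protocol's own AE definition, and everything at issue happens before randomisation.

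These points narrow the concern without removing it. The existing records give a reason or a diagnosis, not an adverse event. An earlier consent step in the flow chart would settle the consent timing but would leave the adverse event window where it is. Consistency with the AE definition does not help, because the definition is itself part of what leaves the interval uncovered.

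**Conclusion.** The point holds in a limited form. For patients who stop an excluded drug in order to enter, events over at least 7 or at least 14 days of study time are not collected as adverse events, and it is unclear whether SAE reporting applies. The scheduled observation that follows is 1 + 12 + 1 = 14 weeks. Separately, the consent mark in Table 1 conflicts with inclusion criterion 1 for these patients.

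The number affected cannot be derived. The documents give no share of patients who stop a drug for the study, and the previous dopamine agonist subgroup would not supply it, because it also includes patients who stopped earlier for other reasons. No event rate is given.

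A reader might go further and suspect bias between arms. The documents do not support this: the washout precedes randomisation, and the primary analysis is unaffected. The absence of a monitoring committee (Protocol 10.1) adds little for the same reason. This is a gap in safety recording that should be closed, not a threat to the efficacy result. The conclusion assumes that sites follow 5.4.2 and 5.5.1 as written.

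**What to change.** 1. Reconcile the consent timing in Table 1, and in the matching SAP schedule, with inclusion criterion 1 for patients who stop a drug in order to enter.
2. Amend Protocol 5.4.2 and 5.5.1 so that SAEs, and AEs the investigator links to stopping medication for the study, are recorded from informed consent. The AE definition needs an explicit extension, since these events precede study drug. Align 5.5.5 and 5.5.6 so that the start of SAE reporting is stated once.
3. Add these events to the eCRF items in Protocol 8.1.1 for patients withdrawn before run-in.
4. In the SAP, report them in a pre-treatment listing separate from TEAEs. The TEAE definition does not change.

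No new field for the date of stopping is needed: Protocol 5.1.3.1 already collects therapy dates for medication used in the 28 days before run-in. Washout lengths and drug restrictions are left unchanged.

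The cost is amended wording and slightly more data entry at sites. No extra visit is required, because the questions can be asked at the Week -1 visit or when the reason for withdrawal is recorded.
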